## **11.2. Sample Size and Power Calculations**

The primary endpoint is difference between treatments in the proportion of surviving subjects off vasopressors, the ventilator, and dialysis on Day 14. For Part 1, the power for the study is computed for the expected increase in proportion of surviving subjects without these supports at Day 14 after start of study treatment. A total sample size of N=54 has ~80% power to yield a statistically significant (alpha=0.2 1-sided) difference if the TRUE underlying proportions are 20% and 5% for placebo plus SOC and rhu-pGSN plus SOC, respectively. The minimum OBSERVED difference from placebo plus SOC proportion 20% that yields statistical significance is 8.4% (20% vs 11.6%). As this is a pilot Phase 2 POC trial in an infection with no approved therapy and false negative error (100% minus power) is equally as important as false positive error, the one-sided type 1 error is set at 0.2. Thus, the trial is adequately powered for its primary POC objective.

For Part 2, a sample size of 20 subjects was chosen to generate an estimate of any clinically relevant treatment effect.

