4.2 Sample Size Justification

The primary endpoint is difference between treatments in the proportion of surviving subjects off vasopressors, the ventilator, and dialysis on Day 14. Here the power for the study is computed for the expected increase in proportion of surviving subjects without these supports at Day 14 after start of study treatment. A total sample size of N=54 has ~80% power to yield a statistically significant (alpha=0.2 1-sided) difference if the TRUE underlying proportions are 20% and 5% for placebo plus SOC and rhu-pGSN plus SOC, respectively. The minimum OBSERVED difference from placebo plus SOC proportion 20% that yields statistical significance is 8.4% (20% vs 11.6%). As this is a pilot Phase 2 POC trial in an infection with no approved therapy and false negative error (100% minus power) is equally as important as false positive error, the one-sided type 1 error is set at 0.2. Thus, the trial is adequately powered for its primary POC objective.

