8.1 General Conventions

All analyses will be done using SAS (version 9.4, SAS Institute Inc., Cary, NC, USA).

Efficacy and Safety endpoints will be analyzed in a descriptive manner. Continuous data will be reported using the following descriptive statistics:

1. Number of observations (n)
2. Mean and Standard deviation (SD)
3. Interquartile Range (IQR)
4. Minimum (min) and Maximum (max)
5. Median

In addition:

6. Geometric mean & Standard deviation
7. Coefficient of variation (CV%)
8. Geometric CV%

will be reported for plasma concentration data and PK parameters. Categorical data will be presented using frequency (n = number of subjects; m = number of events) and percentage (%).

Listings will be provided for all data recorded in eCRF to study subject profiles. All listings will be sorted by treatment, subject ID, and date (if applicable). Unscheduled visit data will only be listed and not included in summaries.

All p-values will be displayed to four decimal places, with p-values less than 0.0001 presented as '<0.0001' and p-values greater than 0.9999 presented as '>0.9999'. Minimum and maximum values will be reported in the units of collection with 3 decimals being maximum value; the mean will be presented with 1 decimal place more and the standard deviation 2 decimal places more than the units of collection. Percentages for categorical summaries will be represented to 1 decimal place.

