12.9.1 Primary Efficacy analysis

12.9.1.1 Proportion of Subjects Alive on Day 14

Number and percentage of subjects alive on Day 14 without the following will be summarized. Percentages will be based on the corresponding analysis set. Subjects who discontinued from the study early or whose survival status is inconclusive on Day 14 will be considered as failure (Not Alive).

- Ongoing use of vasopressors
- Ongoing intubation/mechanical ventilation
- New ongoing need for dialysis/renal replacement therapy (RRT)

The proportion of subjects alive will be compared across treatment arms using a Cochran-Mantel-Haenszel (CMH) method. The common Risk Difference along with associated 80% CI will be reported. Unadjusted p-value for testing the null hypothesis that there is no strong correlation between treatment and subject status will also be reported. As this is a pilot Phase 2 proof-of-concept (POC) trial in an infection with no approved therapy and false negative error (100% minus power) is equally as important as false positive error, the one-sided type 1 error is set at 0.2.

Reference SAS Program:

```
proc freq data= ;
  tables <status>*<treatment> / cmh riskdiff(common) alpha=0.2;
run;
```

The analyses will be based on FAS and repeated for Per-Protocol Analysis Set.

In DDP: Tables 14.2.1.1 and 14.2.1.2, Listing 16.2.6.2, 16.2.6.3, and 16.2.6.4

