12.9.2.4 Proportion of Subjects Discharged

Number and percentage of subjects who were discharged on or before Days 14, 28, 60 and 90 will be summarized by treatment group. Proportions within each treatment group along with 95% CI will be

provided using Clopper-Pearson method for each visit. Risk Differences between treatment groups and p-value from testing the null hypothesis that there are no differences between treatment groups will be reported based on Fisher's Exact test. The summary will be based on FAS and repeated for Per-Protocol Analysis Set.

Reference SAS Program:

```
/* 95% CI for binomial (exact Clopper-Pearson) */

proc freq Data=XXX alpha=0.05;
  by treatment;
  tables flag/binomial(level='1' exact);
run;

/* 95% CI for risk difference and p-value from Fisher's test */

proc freq Data=XXX alpha=0.05;
  tables treatment*flag/riskdiff(cl=exact);
  exact riskdiff fisher;
run;
```

In DDP: Tables 14.2.5.1 and 14.2.5.2 and Listing 16.2.6.2

12.9.2.5 Hospitalization due to COVID 19

Number and percentage of subjects re-admitted to an acute-care hospital and subjects who are ongoing hospitalization at Day 14 will be summarized. Descriptive summaries for Duration of COVID-19 illness before hospitalization and cumulative number of hospitalization days will also be summarized.

Number and percentage of subjects who have been to the ICU and subjects who are still in ICU at End of Study will be summarized. Descriptive summary for cumulative number of ICU days will also be summarized.

Number and percentage of subjects who had Intubation / Mechanical Ventilations and subjects who are still in Intubation / Mechanical Ventilations at End of Study will be summarized. Descriptive summary for cumulative number of Intubation / Mechanical Ventilations days will also be summarized.

All summaries will be based on FAS and per-protocol analysis sets. Percentages will be based on the corresponding analysis sets.

In DDP: Table 14.2.6.1 and Table 14.2.6.2

Hospitalization, ICU and Intubation / Mechanical Ventilations will be listed by subject.

In DDP: Listings 16.2.6.2, 16.2.6.3, and 16.2.6.4

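### The primary-analysis outputs in SAP 12.9.1.1 (two-sided 80% CI, non-directional CMH p-value, status-by-treatment table) do not match its one-sided 0.20 test

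*SAP*

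**What the plan says.** SAP 12.9.1.1 compares arms on the proportion alive at Day 14 without vasopressors, ventilation or new dialysis, using the CMH method. It states the level: "the one-sided type 1 error is set at 0.2". It asks for two results:

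- an interval: "The common Risk Difference along with associated 80% CI will be reported"
- a p-value: "Unadjusted p-value for testing the null hypothesis that there is no strong correlation between treatment and subject status will also be reported"

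The table statement in its reference program is "tables <status>*<treatment> / cmh riskdiff(common) alpha=0.2". SAP 12.9.2.3 repeats this analysis for Days 7, 14, 28, 60 and 90, with ICU residence added to the criteria.

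The design sections use the same test. Protocol 11.2 states: "A total sample size of N=54 has ~80% power to yield a statistically significant (alpha=0.2 1-sided) difference". SAP 4.2 repeats this. Both speak of an expected increase in survival without support, and both put the smallest significant observed difference at 8.4 points (20% against 11.6%).

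Two other places bear on the point. For discharge, SAP 12.9.2.4 puts treatment in the rows; its table statement begins "tables treatment*flag/riskdiff(cl=exact". SAP 8.1 says of all endpoints: "Efficacy and Safety endpoints will be analyzed in a descriptive manner".

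**The concern.** The level and direction of the primary test can be recovered from SAP 12.9.1.1 read with SAP 4.2 and protocol 11.2. The outputs do not carry that test through, in three respects.

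- **(a) Interval.** A two-sided 80% CI leaves 10% in each tail, so it corresponds to one-sided 0.10.
- **(b) P-value.** The CMH chi-square has no direction. The SAP does not say that its p-value is halved, or that the risk difference must favour rhu-pGSN.
- **(c) Table layout.** With status in the rows, a row-wise risk difference is the share of one arm among failures minus its share among successes. That is not the difference between arms in the proportion succeeding.

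Under (a) and (b), a trial that meets its planned test can be reported with a p-value above 0.20 and an interval that includes 0, and no sentence says how to read them together. Under (c), the printed primary estimate and its interval would be for the wrong quantity.

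**Working it through.** **Inputs.** One-sided 0.20, N=54 (27 per arm), and rates of 20% placebo and 5% rhu-pGSN (SAP 4.2, protocol 11.2); 30 per arm in Part 1 (protocol 7.1). I read 20% and 5% as failure rates. This is an assumption: the text introduces them as proportions surviving without support, but the expected benefit is an increase. Differences are placebo minus rhu-pGSN failures, so positive values favour rhu-pGSN.

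**1. The plan's own figures.** Normal formula with pooled null variance, mean rate 0.125:

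power = Φ{[0.15√n − z·√(2 × 0.125 × 0.875)] / √(0.20 × 0.80 + 0.05 × 0.95)}

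At n=27 and z=0.8416: (0.7794 − 0.3936)/0.4555 = 0.847, so power is 80.1%. The stated figure reproduces. For 20% against 11.6%, the pooled SE is √(0.158 × 0.842 × 2/27) = 0.0993 and z = 0.084/0.0993 = 0.846, so the one-sided p is 0.199. The 8.4-point threshold also reproduces. It rests on the normal formula: the N−1 variance in the CMH statistic gives 0.201 for these rounded rates, just outside the test. The example below therefore uses whole counts.

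**2. A result that meets the test: 6/30 placebo, 3/30 rhu-pGSN failures.**

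- CMH: expected placebo failures are 4.5; variance is 30 × 30 × 9 × 51/(60² × 59) = 1.945; z = 1.5/√1.945 = 1.076.
- One-sided p = 0.141, which meets 0.20. The p-value as printed is 0.282.
- Between-arm SE = √[(0.2 × 0.8 + 0.1 × 0.9)/30] = 0.0913.
- 80% CI: 10.0 ± 1.2816 × 9.13 = -1.7 to +21.7 points, which includes 0.
- 60% CI: 10.0 ± 0.8416 × 9.13 = +2.3 to +17.7 points, which agrees with the test.

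**3. The same data with status in the rows.** Placebo share among failures is 6/9 = 66.7%; among successes it is 24/51 = 47.1%. The difference is 19.6 points instead of 10.0, with a Wald 80% CI of about -2.4 to +41.6. At the design rates the status-row difference is 0.20/0.25 − 0.80/1.75 = 80.0% − 45.7% = 34.3 points instead of 15. The CMH p-value is the same in either layout.

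**4. How often the outputs and the test diverge.** I summed exact binomial probabilities at 20% against 5% over all results with one-sided CMH p < 0.20 and a between-arm 80% CI that includes 0. The total is 0.154 at 27 per arm and 0.140 at 30 per arm.

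**5. Power, only if success were read from the 80% CI or from an unhalved p < 0.20.** The formula in step 1 with z = 1.2816:

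| Per arm | One-sided 0.20 (stated) | One-sided 0.10 |
|---|---|---|
| 27 | 80.1% | 65.4% |
| 30 | 82.6% | 68.7% |

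**The case against.** The strongest reply is that the test is not in doubt. SAP 12.9.1.1 states the one-sided level directly after describing the p-value, the design sections give the direction, and SAP 8.2 names a single primary efficacy hypothesis. Nothing makes the 80% CI a decision rule, and SAP 8.1 calls the efficacy analysis descriptive, so the interval may be meant only as a measure of precision. This largely stands. It means that the documents are not silent on level and direction, and that the gap in (a) and (b) is one of matching and labelling. It does not close the gap: 12.9.1.1 neither calls the interval descriptive nor says that the p-value is halved. SAP 12.9.2.6 shows that the SAP can state sidedness and level when it chooses to.

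A reader might infer that the trial is underpowered, at about 65%. The documents do not support that. Power is about 80% for the test they state, and the lower figures belong to a decision rule that they do not adopt.

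On (c), the program is labelled as a reference and uses placeholders, the text says that arms are compared, and the row-wise convention is not written in the documents. These points make (c) conditional on the code being run as written. The treatment-by-flag layout in SAP 12.9.2.4 supports the convention. The Data Display Plan was not available and may settle some of this.

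**Conclusion.** The point holds as a mismatch between the stated primary test and its specified outputs, and it should be fixed. At the design rates, about one trial in seven would meet the planned test while its between-arm 80% CI includes 0. This rests on reading 20% and 5% as failure rates and on Wald intervals. The table layout is a separate defect: if the code is run as written under the row-wise convention, the estimate and interval are not for the difference between arms, although the p-value is unaffected. The sample size, the stated power and the level of the planned test need no change.

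**What to change.** Before unblinding, amend SAP 12.9.1.1; the changes then carry into 12.9.2.3.

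1. Tabulate treatment by status, as 12.9.2.4 does, so that the risk difference compares arms. Changing alpha alone would not give the intended interval.
2. State that success is one-sided CMH p < 0.20 favouring rhu-pGSN, that is, half the two-sided p when the difference favours rhu-pGSN.
3. Report the matching two-sided 60% CI (alpha=0.4) or a one-sided 80% bound, and label any 80% CI as descriptive.

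A statement on exact size is optional. If one is made, it should give the full range: about 0.20 to 0.25 for common failure rates of 5% to 30%, highest at 5%. If the Data Display Plan already fixes any of these items, cite it in 12.9.1.1.

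The cost is a few sentences and two code edits, with no added patients. The drawback is that a 60% CI is less familiar to readers.

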8.2 Multiplicity Adjustment

Since there is only one primary efficacy hypothesis defined in the study as per the protocol (difference between treatments in the proportion of surviving patients off vasopressors, the ventilator, and dialysis on Day 14), multiplicity adjustment is not required for the primary endpoint. Hypothesis tests for secondary endpoints will be performed, and caution must be taken when interpreting these results. Adjusted p-values using Bonferroni method may be reported from post-hoc tests if deemed necessary.

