11.6 Replacement Subjects

If one of the eligible subjects is included in the study as replacement, then the subject will be flagged as replacement subject with subject ID of the replaced subject. For example, if subject XXXY is replaced, then replacement subject XXXX will be flagged as 'Replacement for XXXY'. These flags will be used only in listings, and not in any analyses. Summaries will include data for replacement subjects like any other subject in that treatment group.

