12.9.2.2.4 Listing

Death Details will be listed by subject.

In DDP: Listing 16.2.7.4

12.9.2.3 Proportion of Subjects Alive on Days 7, 14, 28, 60 and 90

Number and percentage of subjects alive on Days 7, 14, 28, 60 and 90 without the following will be summarized. Percentages will be based on FAS. Subjects who discontinued from the study early or whose survival status is inconclusive on respective day will be considered as failure (Not Alive).

- Ongoing use of vasopressors
- Ongoing intubation/mechanical ventilation
- Ongoing residence in an ICU
- New ongoing need for dialysis/renal replacement therapy (RRT)

The analyses described in Section 12.9.1.1 will be repeated for each day as part of secondary analyses.

In DDP: Tables 14.2.4.1 and 14.2.4.2, Listing 16.2.6.2, 16.2.6.3, 16.2.6.4

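### The reference program for the primary endpoint puts outcome status in the rows, so its risk difference and 80% CI are not the between-treatment difference the SAP defines

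*SAP*

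**What the plan says.** The target quantity is stated consistently. SAP 4.2: "The primary endpoint is difference between treatments in the proportion of surviving subjects off vasopressors, the ventilator, and dialysis on Day 14". SAP 8.2 names a single primary hypothesis, the "difference between treatments in the proportion of surviving patients off vasopressors, the ventilator, and dialysis on Day 14". SAP 12.9.1.1 follows with "The proportion of subjects alive will be compared across treatment arms using a Cochran-Mantel-Haenszel (CMH) method" and "The common Risk Difference along with associated 80% CI will be reported".

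The reference program in the same section reads "tables <status>*<treatment> / cmh riskdiff(common) alpha=0.2". Status is the row variable and treatment the column variable. Nothing in the SAP swaps them back or asks for a column-wise contrast.

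For the discharge endpoint, SAP 12.9.2.4 uses the opposite order: "tables treatment*flag/riskdiff(cl=exact", with treatment in rows.

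SAP 12.9.2.3 carries the primary method to Days 7, 14, 28, 60 and 90: "The analyses described in Section 12.9.1.1 will be repeated for each day as part of secondary analyses".

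On a smaller, related matter, Protocol 11.1 specifies a stratified CMH test and logistic regression for Part 1 binary endpoints, without naming strata or covariates. The primary analysis in SAP 12.9.1.1 has no stratum and the SAP contains no logistic regression. SAP Section 13 lists two changes to the planned analyses, and neither is this one.

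**The concern.** In a two-way table, RISKDIFF subtracts the row 2 risk from the row 1 risk. With status in rows, the risks are the proportions of successes and of failures who received rhu-pGSN. Their difference describes how treatment is distributed within outcome groups, not how outcome differs between treatments.

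The p-value is not at stake, because the CMH statistic is symmetric in rows and columns. What is at stake is the primary effect estimate and its 80% interval. In a proof-of-concept trial these are the figures passed on to later planning. The per-arm percentages in the same table would not reproduce the reported difference.

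**Working it through.** **Inputs.** Total N=54 (27 per arm), one-sided alpha 0.2, rates 20% (placebo) and 5% (rhu-pGSN): SAP 4.2. Planned Part 1 size 30 per arm: Protocol 7.1. Allocation 1:1: SAP 4.6. The 20% and 5% are taken as failure rates, so success is 80% and 95%. The documents do not say this, but read as success rates they would favour placebo.

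**The plan's own figures.** Pooled z-test, no continuity correction, pooled rate 0.125:

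- Power = Φ{[0.15 − 0.8416·√(2·0.125·0.875/27)] / √[(0.2·0.8 + 0.05·0.95)/27]} = Φ{(0.15 − 0.0758)/0.0877} = 80.1%, against a stated ~80%.
- Minimum significant difference from 20%: 8.36 points (20% vs 11.64%), against a stated 8.4 (20% vs 11.6%).

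The design was therefore sized on the between-arm difference.

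**Algebra.** Let a, b be successes and c, d failures on rhu-pGSN and placebo, with n1 = a+c, n2 = b+d, N = n1+n2.

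- Treatment in rows: a/n1 − b/n2 = (ad − bc)/(n1·n2).
- Status in rows: a/(a+b) − c/(c+d) = (ad − bc)/[(a+b)(c+d)].
- Ratio, coded to true: r(1−r)/[p(1−p)], with r = n1/N and p = (a+b)/N.

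The sign in SAS depends on level order; here rhu-pGSN and success come first. With equal arms the ratio is 1/[4p(1−p)]:

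| Pooled success p | Ratio |
|---|---|
| 0.50 | 1.00 |
| 0.70 | 1.19 |
| 0.80 | 1.56 |
| 0.875 (design rates) | 2.29 |
| 0.90 | 2.78 |

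**Design rates, 27 per arm (expected counts).** a=25.65, b=21.6, c=1.35, d=5.4, so ad − bc = 138.51 − 29.16 = 109.35.

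- Treatment in rows: 109.35/729 = 15.0 points; Wald 80% CI 3.8 to 26.2.
- Status in rows: 109.35/(47.25·6.75) = 34.3 points; Wald 80% CI 12.5 to 56.1.
- CMH z = 1.651 in both layouts (one-sided p=0.049).

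**Illustrative counts, 28/30 vs 25/30.** ad − bc = 140 − 50 = 90.

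- Treatment in rows: 90/900 = 10.0 points (−0.5 to 20.5).
- Status in rows: 90/(53·7) = 24.3 points (0.7 to 47.8).
- CMH z = 1.196 in both layouts (one-sided p=0.116).

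**Unequal arms.** The FAS is formed by actual drug received (SAP 10.4), and of replacements SAP 11.6 says "Summaries will include data for replacement subjects like any other subject in that treatment group". Arms need not be exactly equal. A true 15.0 points becomes 33.0 at 28:32 (rhu-pGSN:placebo) and 35.4 at 32:28. Extreme splits of 20:40 and 40:20, shown only to bound the effect, give 26.1 and 37.0.

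**Coverage.** Exact binomial enumeration of all outcomes, 30 per arm, 95% vs 80% success, 80% Wald limits:

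| | Treatment in rows | Status in rows |
|---|---|---|
| Mean estimate (points) | 15.0 | 34.7 |
| Interval covers the true 15 points | 76.3% | 45.6% |
| Lower limit above zero | 71.9% | 76.6% |

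At 27 per arm, coverage is 76.9% and 46.8%.

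**The case against.** The block is labelled a reference program and consists of placeholders. The surrounding text is unambiguous, and a 34-point difference printed beside 95% and 80% would probably be noticed. The final code and the table shells in the Data Display Plan are not among the documents. All of this stands, and it limits the severity. It does not remove the conflict, because this is the only program the SAP gives for the primary estimate, and the plan should not rely on someone catching the mismatch.

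The distortion also depends on the observed rates. It vanishes at 50% pooled success in equal arms and is 1.19 at 70%. The 2.29 rests on reading 5% and 20% as failure rates. The factor is symmetric in p, so the other reading reverses the sign and leaves the size unchanged. The extreme splits are not expected under 1:1 allocation with replacement in the original arm (Protocol 6.9).

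Exclusion of zero by the 80% CI is not the trial's decision rule. A two-sided 80% interval corresponds to a one-sided 0.1 test, while the plan tests at one-sided 0.2. For 28/30 vs 25/30 the test is positive (p=0.116), although the correctly oriented interval includes zero. In the enumeration at 30 per arm the test is positive in 85.9% of trials, and the coded lower limit agrees with it slightly more often than the correct one (90.7% vs 86.0%). The shift across zero therefore shows that the interval changes; it is not evidence of a false positive claim.

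Finally, stratification is a separate matter from row order. The Protocol synopsis says that subjects are not formally stratified by severity, and SAP 12.9.2.3.1 already has a CMH analysis controlling for baseline WHO score, though on the composite that adds ICU residence. What remains is that Section 13 does not declare the departure from Protocol 11.1.

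**Conclusion.** The concern holds. Followed literally, the program in SAP 12.9.1.1 gives a primary effect estimate and 80% CI for a different quantity from the one that SAP 4.2, 8.2 and the text of 12.9.1.1 define. At the design rates, read as failure rates and with equal arms, the estimate is about 2.3 times too large (34.3 instead of 15.0 points). Its interval covers the true difference in fewer than half of trials. The hypothesis test is unaffected.

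The same order carries into the Day 7 to 90 repeats. The size of the distortion there is unknown, because the documents give no rate for the composite that includes ICU residence. The undeclared absence of stratification and logistic regression is a minor point.

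**What to change.** In SAP 12.9.1.1, swap the two variables so that the table request is `<treatment>*<status>`, keep the options, and state that rhu-pGSN is row 1 and success is column 1. With no stratum the common risk difference is simply the difference between the two arms. Use the same order in 12.9.2.3. If 12.9.2.3.1 reuses the code, do the same there, with baseline WHO score as stratum and the 95% limits that section specifies.

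If outputs exist, rerun Tables 14.2.1.1, 14.2.1.2, 14.2.4.1 and 14.2.4.2, and also 14.2.4.3 and 14.2.4.4 if they used this code.

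In Section 13, declare that the primary analysis is unstratified and that no logistic regression is planned, as departures from Protocol 11.1.

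Optionally, add a CMH analysis of the primary flag (Flag 01) stratified by baseline WHO score as supportive. Making it primary is not required. In 40,000 simulated trials at 30 per arm (assumed WHO 4/5/6 mix 40/30/30, rhu-pGSN failure one quarter of placebo), power moved from 0.860 to 0.870 with placebo failure of 5/10/50% across the scores. With 12/20/31% it moved from 0.858 to 0.842.

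The cost is one line of SAS, one or two sentences in Section 13, and four to six reruns if outputs exist. The optional analysis adds one entry in SAP 16.1 and one table per analysis set; baseline WHO score is already collected.
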